#### **8.2.4. Objective Response Rate (ORR)**

ORR is defined as the proportion of patients with a BOR of CR or PR after randomization.

[figure not shown]

#### **8.2.5. Duration of Objective Response (DOR)**

DOR is defined as the time from the earliest date when a tumor response of CR or PR is observed until the date of the first occurrence of disease progression or death due to any cause: Patients who don't have disease progression or have not died on or prior to the analysis cutoff date will be censored at the last adequate disease assessment date, or the earliest date of the tumor response of CR or PR observed if no disease assessment is available afterwards. See [Section 8.2.1](#) for the definition of disease progression and adequate disease assessment.

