10.4.2. Phase 2 Efficacy Analysis

Investigational Product: IMU-131
Protocol Identifier: IMU.ACS.001
Protocol Version: Protocol Global Amendment #5, 27 September 2023

Analysis of the primary endpoint, OS, and secondary endpoint, PFS, will be performed using the ITT population. Additional secondary and exploratory analyses of efficacy endpoints will be performed using the ITT, FAS, and/or the EVAL sets. Ancillary analyses of select efficacy endpoints may also be performed using the PP set.

The log-rank method will be used to estimate the secondary efficacy parameter of PFS. Analyses of TTP, DCR, ORR, DOR and CTS will be performed using the same methods as described for PFS. The blinded central review disease response assessments will be used as the primary measure for these analyses, and the Investigator disease response assessments will be used as supportive measures for these analyses.

Patients who are continuing in the study at the time of the primary final analysis will continue to be followed per the schedule of assessments until completion of the study; a supplementary analysis may be produced to reflect any additional data collected after the primary final analysis.

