**Table 8-1 Censoring Conventions for PFS**

Situation	Date of Progression or Censoring	Outcome
Disease progression, and time interval between progression date and previous tumor assessment date with progression-free response is less than or equal to 98 days	Earliest of: 

• Date of first tumor assessment showing new lesion

• Date of first tumor assessment with overall response of PD

	Event
Disease progression, and time interval between the progression date and the previous tumor assessment date with progression-free response is greater than 98 days.	Latest of: 

• the last progression-free assessment date

• randomization date

	Censored
Death without any post-baseline radiological assessment, and time interval between death	Death date	Event

date and randomization date is less than or equal to 98 days		
Death without any post-baseline radiological assessment, and time interval between death date and randomization date is greater than 98 days	Randomization date	Censored
Death before documented progression, and time interval between death date and previous tumor assessment date with progression-free response is less than or equal to 98 days	Death date	Event
Death before documented progression, and time interval between death date and previous tumor assessment date with progression-free response is greater than 98 days	The last progression-free assessment date	Censored
No death or disease progression, no treatment discontinuation due to symptomatic deterioration, and no subsequent anti-cancer therapy (i.e., systemic anti-cancer therapy, anti-cancer surgery, curative radiotherapy).	Latest of 
 
• the last progression-free assessment date
 
• randomization date
 
	Censored
Subsequent anti-cancer treatment (i.e., systemic anti-cancer therapy, anti-cancer surgery, radiotherapy) started prior to progression	Latest of 
 
• the last progression-free assessment date prior to start of anti-cancer treatment
 
• randomization date
 
	Censored
Treatment discontinuation due to symptomatic deterioration prior to disease progression	Latest of 
 
• the last progression-free assessment date before treatment discontinuation date
 
• randomization date
 
	Censored

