An adequate disease assessment is a schedule or unscheduled assessment where the overall tumor assessment as assessed by blinded central reviewers is not missing and not unevaluable.

Progression-free survival is calculated as follows.

PFS = Analysis date defined above – randomization date + 1

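### Duration of response has its own censoring rule, so responders censored early for PFS stay at risk for DOR, including time on another anti-cancer therapy

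*SAP*

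**What the plan says.** SAP 8.2.5 starts DOR at the earliest CR or PR and ends it at the first of progression or death from any cause. Its only censoring rule covers patients who have not progressed or "have not died on or prior to the analysis cutoff date will be censored at the last adequate disease assessment date", with the response date as fallback if there is no later assessment. It points back to 8.2.1 only "for the definition of disease progression and adequate disease assessment". Under 8.2.1 an assessment is adequate when "the overall tumor assessment as assessed by blinded central reviewers is not missing and not unevaluable", so nothing cuts the series at the start of new therapy. The opening of SAP section 8 uses all assessments up to cutoff or end of study unless otherwise specified.

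Table 8-1 censors PFS in four situations that can apply to a responder:

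- "Subsequent anti-cancer treatment (i.e., systemic anti-cancer therapy, anti-cancer surgery, radiotherapy) started prior to progression": censored at "the last progression-free assessment date prior to start of anti-cancer treatment" (or the randomization date, if later).
- "Disease progression, and time interval between the progression date and the previous tumor assessment date with progression-free response is greater than 98 days": censored at the last progression-free assessment.
- "Death before documented progression, and time interval between death date and previous tumor assessment date with progression-free response is greater than 98 days": censored at the last progression-free assessment.
- Treatment stopped for symptomatic deterioration before progression: censored at the last progression-free assessment before the stop.

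Table 8-2 lists the same situations for TTP and also censors them. Protocol 10.4.2 states: "Analyses of TTP, DCR, ORR, DOR and CTS will be performed using the same methods as described for PFS".

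**The concern.** For a responder, one would expect DOR to be the part of PFS that follows first response. Here the two endpoints end by different rules, and neither document says so. The same patient, on the same scans, can be censored for PFS and count as an event for DOR. The DOR interval can also contain months on a therapy that is not part of the randomized treatment.

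The situation can arise in this trial. Patients who end study treatment before progression go on being scanned every 42 days, and later anti-cancer treatment is recorded (SAP 3.1, Post-treatment Follow-up Period; protocol 8.12). At stake are a DOR estimate that credits later therapy to the study arm and a DOR listing that cannot be reconciled with the PFS listing. SAP 8.2.6 carries the same rule into DOR by investigator assessment.

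**Working it through.** The plan gives no figure to reproduce, and no power or alpha enters. The check applies the two written rules to constructed patients.

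**Inputs**
- Scans at Days 42, 84, 126 and every 42 days after (SAP Appendix 1, note E).
- Gap limit of 98 days (Table 8-1).
- PFS = analysis date − randomization date + 1 (SAP 8.2.1), with randomization at Day 0.
- DOR = end date − first CR/PR date. The visible text gives no day formula for DOR; add 1 for an inclusive count.
- Response, therapy, progression and death dates are illustrative.

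| Case (study days) | PFS, Table 8-1 | DOR, SAP 8.2.5 | DOR with PFS end date and status |
|---|---|---|---|
| A. PR 84, last scan before new therapy 126, new therapy 150, PD 336 | 126 + 1 = 127, censored | 336 − 84 = 252, event | 126 − 84 = 42, censored |
| B. PR 42, scans at 84 and 126 missed, PD 168 (gap 168 − 42 = 126) | 42 + 1 = 43, censored | 168 − 42 = 126, event | 42 − 42 = 0, censored |
| C. PR and last scan 42, death 200 (gap 200 − 42 = 158) | 42 + 1 = 43, censored | 200 − 42 = 158, event | 42 − 42 = 0, censored |
| D. As A, but treatment stopped at 150 for symptomatic deterioration and no new therapy | 126 + 1 = 127, censored | 336 − 84 = 252, event | 126 − 84 = 42, censored |
| E. PR 42, last scan before new therapy 126, new therapy 127, no PD, last scan 378 | 126 + 1 = 127, censored | 378 − 42 = 336, censored | 126 − 42 = 84, censored |
| F. Boundary: PR 42, PD 140 (gap 140 − 42 = 98) | 140 + 1 = 141, event | 140 − 42 = 98, event | 140 − 42 = 98, event |
| G. Ordinary: PR 42, last progression-free scan 126, PD 168 | 168 + 1 = 169, event | 168 − 42 = 126, event | 168 − 42 = 126, event |

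In case A, 336 − 150 = 186 of the 252 DOR days fall after the new therapy began (inclusive DOR: 253 days). Cases F and G show that the rules agree when Table 8-1 does not censor early. The discrepancy is confined to the four situations listed above.

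**How many responders are involved.** With 36 patients randomized 1:1, each arm has 18. At the response rates that protocol 1.2 quotes for the two arms of the phase 3 trastuzumab trial, 18 × 0.345 = 6.2 and 18 × 0.473 = 8.5, so roughly 6 to 9 responders per arm. One patient is then 1/9 = 11% to 1/6 = 17% of an arm's responders. The effect on median DOR was not calculated; it depends on the other patients' times.

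**A trap in aligning the two rules.** SAP 8.2.3 derives best response from all assessments to cutoff, so a first PR can come after the PFS censoring date. With last scan before new therapy at Day 126, new therapy at Day 127 and first PR at Day 168, simply reusing the PFS date gives 126 − 168 = −42 days. Late responses therefore have to be kept out explicitly.

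**The case against.** The best defence is that counting every progression or death is a legitimate choice. It follows the endpoint definition in both documents and the default of using all assessments, and censoring at new therapy can itself be informative. That stands. The defect is that DOR departs from PFS and TTP without saying so, while the protocol says the methods are the same.

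Several stronger readings are tempting, and the documents do not support them.

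- *Surgery.* A reader might infer that surgery after a good response also splits the endpoints. SAP 8.2.1 treats surgery after downstaging as normal care and runs PFS on to confirmed progression, so PFS and DOR agree there. Table 8-1 lists anti-cancer surgery without that exception and should carry it.
- *Censoring of living progressors.* Read literally, the *or* in the SAP 8.2.5 censoring sentence censors anyone lacking either event, including a patient who has progressed and is alive. The definition just before it ends DOR at the first of the two, so this is a slip of wording.
- *A planned log-rank test on responders.* The protocol sentence also covers two proportions and a percentage change, so it cannot send everything it lists to a log-rank test. The DOR analysis method may stand in redacted SAP text. Whether a test is planned is not established.
- *DOR truly longer than PFS.* In cases A to D a censored time, which is only a lower bound, is set beside an event time. What these cases show is inconsistent status and end dates.

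It is also fair that the patients are invented and the response rates come from another trial.

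**Conclusion.** The point holds for four situations: new anti-cancer therapy before progression, progression after a gap over 98 days, death after such a gap, and stopping for symptomatic deterioration. In each, PFS is censored early and the responder stays at risk for DOR. In the main illustration that is 127 days censored against an event at 252 days. This does not fit protocol 10.4.2, if the same methods are taken to include the event and censoring rules.

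The conclusion rests on the visible text of SAP 8.2.5, where the censoring sentence is complete. The frequency of such patients is unknown, so the overall effect on DOR cannot be sized. With an assumed 6 to 9 responders per arm, even one is a noticeable share. DOR is secondary and the primary OS analysis is untouched. The SAP should be corrected, but the trial's main conclusion does not depend on it.

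**What to change.** Replace the censoring sentence in SAP 8.2.5, which also removes the *or*/*and* slip, with:

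> DOR runs from the first CR or PR observed on or before the PFS analysis date to the PFS analysis date, and takes its event/censor status from Table 8-1. Responses first seen after the PFS analysis date do not enter the DOR analysis.

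Then:

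- Add the downstaging-surgery exception to the new-treatment row of Table 8-1.
- If DOR regardless of later therapy and scan gaps is wanted, report it as a labelled sensitivity analysis.
- Label any between-arm DOR comparison descriptive, because responders are not a randomized subset, and align protocol 10.4.2.
- State how many responders counted in ORR are left out of DOR, so that the two tables reconcile.

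The cost is a few sentences in the SAP and one in the protocol. Programming is simpler because the PFS date and status are reused. The downside is that a few responders are censored earlier, so there are slightly fewer DOR events.

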#### **8.2.6. Investigator Disease Assessment (PFS, TTP, DCR, ORR, and DOR)**

 The same analysis method as described in [Section 8.2.1](#), [Section 8.2.2](#), [Section 8.2.3](#), [Section 8.2.4](#), and [Section 8.2.5](#) will be applied.

## 8.2.7. Change in Tumor Size (CTS)

[REDACTED]

## 8.2.8. Sensitivity Analysis

### 8.2.8.1. Clinical Disease Progression

Addition to original disease progression definition, clinical disease progression can be also considered as evidence of disease progression when there is no supportive radiographic assessment of PD. Clinical disease progression is “Progression Disease” leading to treatment discontinuation on eCRF end of treatment page identified by clinical assessment. The date of documented progression disease on eCRF end of treatment page will be used as the event date in a sensitivity analysis. The same full event and censoring rules show in [Table 8-1](#) will be implemented as well but including clinical disease progression as evidence of disease progression when there is no supportive radiographic assessment of PD.

[REDACTED]

### 8.2.8.2. Death Due to Random Cause

Sensitivity analyses will be performed for the endpoints PFS and OS based on ITT set with assumption that patients dying due to any confirmed random event, like COVID-19, will be censored at the date of death. The same inferential analysis described in [section 8.1](#) and [section 8.2.1](#) will be performed for the endpoint OS and PFS, respectively.

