10.7. Sample Size Determination

10.7.1. Phase 1b Sample Size Determination

10.7.2. Phase 2 Sample Size Determination

Investigational Product: IMU-131
Protocol Identifier: IMU.ACS.001
Protocol Version: Protocol Global Amendment #5, 27 September 2023

PFS will be assessed as a secondary outcome with an analysis following 24 evaluable progression events coded using RESIST 1.1 with patients not having a progression being censored at the time of last evaluation for progression or counted as a progression event if death is within 42 days of last evaluation for progression.

Assumptions of accrual time, loss to follow-up, and pooled event rate (both arms combined) used in the sample size calculations may be monitored. The number of patients enrolled, and duration of enrolment and follow-up may be adjusted to achieve the planned number of events at the time of the final analysis of the primary endpoint.

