#### **4.3. Sample Size Calculation**

#### **4.4. Randomization, Stratification, and Blinding**

Patients will be randomized using a permuted block randomization in a 1:1 ratio to receive IMU-131 plus chemotherapy or chemotherapy alone treatment. Randomization will be performed centrally using an Interactive Voice or Web Response System (IxRS) and stratified by tumor stage at screening (III vs. IV).

Phase 2 is an open-label study in which all the personnel will be unblinded except for the central radiography reviewers.

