### 8.1. Primary Efficacy Endpoint

The overall survival (OS) is defined as the time from the randomization to the death due to any cause. Patients who have not died by the time of data cutoff or study end will be censored at the last known alive date, or the data cutoff date for final analysis if the last known alive date is not available yet.

OS time will be calculated as Date of death (or date of last known alive/cutoff date) minus Randomization date + 1.

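### The random-cause sensitivity analysis in SAP 8.2.8.2 censors PFS at the date of death, against Table 8-1, and leaves the list of qualifying causes open

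*SAP*

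**What the plan says.** SAP 8.2.8.2 opens with "Sensitivity analyses will be performed for the endpoints PFS and OS based on ITT set" and sets one rule for both endpoints: "patients dying due to any confirmed random event, like COVID-19, will be censored at the date of death". For the inferential methods it refers back to sections 8.1 and 8.2.1. It lists no causes, sets no standard for confirmation, and says neither who decides nor when.

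The main PFS rules are in Table 8-1. A death before documented progression is an event on the death date if "time interval between death date and previous tumor assessment date with progression-free response is less than or equal to 98 days". If "time interval between death date and previous tumor assessment date with progression-free response is greater than 98 days", the patient is censored at "the last progression-free assessment date". A death with no post-baseline scan is an event within 98 days of randomization; after that it is censored at randomization. Every other censored row also uses the last progression-free assessment or randomization. Table 8-2, for TTP, is different: it censors deaths within 98 days at the death date, but beyond 98 days it too returns to the last assessment or to randomization.

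For the primary endpoint, SAP 8.1 states: "The overall survival (OS) is defined as the time from the randomization to the death due to any cause". On blinding, SAP 4.4 says that in this open-label phase "all the personnel will be unblinded except for the central radiography reviewers". The next sensitivity analysis, 8.2.8.3, allows patients to be moved to a corrected stratum only where it can be credibly argued that treatment arm did not influence the correction. Section 8.2.8.2 carries no such condition.

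**The concern.** OS and PFS need different dates once a death stops being an event. Vital status is observed continuously, so censoring OS at death uses only what is known. Progression is observed only at scans. A patient who dies between scans is known to be progression-free up to the last scan and no further. Censoring PFS at death treats the interval from scan to death as progression-free follow-up, although nobody looked.

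The section is also incomplete. Section 8.2.8.1 states that the full event and censoring rules of Table 8-1 still apply, while 8.2.8.2 refers only to the inferential analysis. It therefore does not say whether the over-98-day rows still hold, or whether a progression documented before a COVID-19 death remains an event. Two programmers could code it differently.

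The open category matters because the trial is small. A check that is meant to show robustness is of little use if its result depends on how a few deaths are labelled, and if the labelling could be settled after results are known. SAP section 12 adds an OS interim analysis at the PFS cutoff, so OS results will exist before the final analysis.

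**Working it through.** **Inputs.** From the SAP: final OS analysis at 24 deaths (section 1); 36 patients randomized 1:1 and 22 months' recruitment (3.1); scans every 42 days (Appendix 1, footnote E); 98-day window (Table 8-1). From Protocol 1.2: median OS of 11.1 months on chemotherapy alone in the phase 3 trastuzumab trial; its use as the control median here is an assumption. Also assumed: exponential times, a median time to progression of 5.5 months, and the non-cancer death rates.

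**The plan's own figure.** The derivation of 24 deaths cannot be reproduced, because alpha, power and target hazard ratio are not visible in the public text. Several sets fit: Schoenfeld's formula gives 24 for HR 0.5, one-sided 20% and 80% power, and 23 for HR 0.4, one-sided 5% and 70% power. Nothing below depends on which was used.

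**Step 1. The rules side by side, for a random-cause death.**

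| Situation | Main PFS, Table 8-1 | 8.2.8.2 read literally | Last-assessment rule |
|---|---|---|---|
| Up to 98 days after last progression-free scan | Event at death | Censored at death | Censored at last scan |
| More than 98 days after it | Censored at last scan | Censored at death | Censored at last scan |
| No post-baseline scan, up to 98 days from randomization | Event at death | Censored at death | Censored at randomization |
| No post-baseline scan, more than 98 days | Censored at randomization | Censored at death | Censored at randomization |
| Progression documented earlier, within 98 days of the previous scan | Event at progression | Not stated | Event at progression |

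In rows 2 and 4 the death is not an event in the main analysis, so a check on deaths counted as events has no reason to move it.

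**Step 2. Unscanned time credited.** With scans on schedule the gap is at most about 42 days and averages about 42/2 = 21. For deaths that the main analysis counts as events it can reach 98 days. For later deaths, on the literal reading, there is no limit: last scan Day 84 and death Day 200 gives 200 − 84 = 116 days. That example requires the Day 126 and Day 168 scans both to be missed.

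**Step 3. Effect on the PFS hazard ratio.** Simulation of 3,000 trials per setting, 18 patients per arm, no treatment effect, scans every 42 days. Censoring at death was compared with censoring at the last scan. Change = exp(|ln(HR at death date / HR at last scan)|) − 1.

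| Mean non-cancer deaths per trial | Mean days credited | Median change | 95th percentile |
|---|---|---|---|
| 1.3 | 21.1 | 0.0% | 2.0% |
| 3.0 | 21.0 | 0.7% | 3.3% |
| 5.6 | 20.8 | 1.2% | 4.7% |

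No scans are missed in this simulation, so it does not cover deaths beyond 98 days.

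**Step 4. Sensitivity of the OS version.** As a ratio of event counts with equal exposure, 12 v 12 gives 1.00. With two vaccine-arm deaths censored, 10/12 = 0.83; with two control deaths censored instead, 12/10 = 1.20. Starting from 10 v 14, 10/14 = 0.71 becomes 8/14 = 0.57. With z = ln(HR)/√(1/d₁ + 1/d₂), z moves from −0.336/0.414 = −0.81 to −0.560/0.443 = −1.26.

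A log-rank simulation (4,000 trials per setting, analysis at the 24th death, randomly chosen vaccine-arm deaths censored) agrees:

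| Vaccine-arm deaths reclassified | 0 | 1 | 2 | 3 |
|---|---|---|---|---|
| True HR 1.0: median HR | 1.00 | 0.92 | 0.83 | 0.75 |
| True HR 1.0: rejection, one-sided 5% | 4.8% | 6.7% | 10.3% | 15.5% |
| True HR 0.7: median HR | 0.70 | 0.63 | 0.57 | 0.51 |
| True HR 0.7: rejection, one-sided 5% | 21% | 27% | 35% | 44% |

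The 5% level is an assumption, and all reclassification is in one arm by construction.

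**The case against.** The strongest reply is that little rides on this. It is a labelled sensitivity analysis; primary OS counts every death, and no visible text ties a decision to 8.2.8.2. That stands, and it limits the point.

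Death-date censoring is not foreign to the SAP either: Table 8-2 uses it for TTP within 98 days. For the same deaths, main PFS already runs to the death date. Both statements are true. But in main PFS the death is itself the event, so progression status at that date does not matter; it matters once the death becomes a censoring. The Table 8-2 precedent also stops at 98 days.

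The 116-day example is extreme. It needs two missed scans and the reading that 8.2.8.2 overrides the over-98-day row. The text allows that reading but does not compel it.

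A reader might infer that unblinded staff will decide which deaths are random. The SAP does not say so: it requires confirmation and names no decision maker, and section 4.4 describes open-label conduct in general. What the text supports is that the process is unspecified and has no safeguard against influence by arm. A reader might also infer that the OS result can be steered. The primary result cannot, by this route. The figures in step 4 are one-directional worst cases, and a genuine COVID-19 death could fall in either arm.

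**Conclusion.** The point holds in a limited form. One censoring date has been applied to two endpoints that need different ones: it is correct for OS and inconsistent with Table 8-1 for PFS. The interplay with the over-98-day rows and with earlier documented progression is left open. The likely numerical effect on the PFS hazard ratio is small, about 0 to 1% at the median and 2 to 5% at the 95th percentile. Those figures assume scans on schedule and the progression and death rates stated above. Missed scans could make the credited time longer.

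The open category of causes is a secondary weakness. With 24 deaths, each one-sided reclassification lowers the sensitivity hazard ratio by roughly 8 to 10%, so this check is fragile unless the causes are fixed in advance. The documents give no evidence that anyone has steered or would steer it. Either version also assumes that random-cause deaths are unrelated to treatment and disease status, which may not hold for COVID-19.

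**What to change.** Amend SAP 8.2.8.2 as follows.

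- **PFS:** censor a random-cause death at the last progression-free assessment before death, or at randomization if there is none. Keep any earlier documented progression as an event. Leave the over-98-day rows of Table 8-1 as they are.
- **OS:** keep the date of death.
- **Causes:** replace the open-ended description with a fixed list of qualifying causes and the evidence needed to confirm each. Set it before the next database lock, apply it identically to both arms without reference to arm, and add a condition like the one in 8.2.8.3.
- **Reporting:** list every reclassified death by arm, with its cause and both analysis dates.

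The PFS change costs a few lines of SAP text and a small programming edit. The list of causes may cost more. It would be tempting to define it by MedDRA terms and assume that no new data are needed, but the documents do not support that. Protocol 9.2 ends AE and SAE reporting 28 days after the last investigational dose and asks for the cause of a later death only if it is likely to be product-related. Protocol 6.4.14 lets survival follow-up rest on phone, email, records or public information. The SAP specifies MedDRA coding for adverse events, medical history and procedures, but not for cause of death. Check first which causes of death in follow-up are on file.

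Separately, Protocol 10.7.2 has a patient "counted as a progression event if death is within 42 days of last evaluation for progression", while the SAP uses 98 days. The two windows should be reconciled, since they determine which deaths are PFS events to begin with.
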